- It is not acceptable for the investigator to send photocopies of the subject's medical records to sponsor/responsible contact research organization (CRO) in lieu of completion of the Events CRF page.
- If specifically requested, the investigator may need to provide additional follow-up
 information, such as discharge summaries, medical records, or extracts from the
 medical records. In this case, all subject identifiers, with the exception of the
 subject number, will be blinded on the copies of the medical records before
 submission to Amgen.
- The investigator will attempt to establish a diagnosis of the event based on signs, symptoms, and/or other clinical information. In such cases, the diagnosis (not the individual signs/symptoms) will be documented as the adverse event/serious adverse event.

Evaluating Adverse Events and Serious Adverse Events

Assessment of Severity

The investigator will make an assessment of severity for each adverse event and serious adverse event reported during the study. The assessment of severity will be based on:

The Amgen Standard Grading Scale as show below:

Grade Definition

Protocol Number: 20200195

Date: 15 April 2022 Page 79 of 99

MILD Aware of sign or symptom, but easily tolerated

MODERATE Discomfort enough to cause interference with usual activity

SEVERE^a Incapacitating with inability to work or do usual activity

a An event is defined as 'serious' when it meets at least 1 of the predefined outcomes as described in the definition of a serious adverse event, NOT when it is rated as severe.

Assessment of Causality

- The investigator is obligated to assess the relationship between investigational product(s) protocol-required therapies, and/or study-mandated activity and/or procedure(s) and each occurrence of each adverse event/serious adverse event.
- Relatedness means that there are facts or reasons to support a relationship between investigational product and the event.
- The investigator will use clinical judgment to determine the relationship.
- Alternative causes, such as underlying disease(s), concomitant therapy, and other
 risk factors, as well as the temporal relationship of the event to study treatment
 administration will be considered and investigated.
- The investigator will also consult the Investigator's Brochure and/or Product Information, for marketed products, in **their** assessment.

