2.1 Objectives and Endpoints/Estimands

Objec	tives	Endpoints			
Prima	Primary				
•	To evaluate the efficacy of apremilast 30 mg twice daily (BID) compared with placebo in subjects with PPP	 Achieving at least 50% reduction from baseline in Palmoplantar Pustulosis Area and Severity Index (PPPASI) total score (PPPASI-50) at week 16 			
Seco	ndary				
•	To evaluate the efficacy of apremilast 30 mg BID compared with placebo in subjects with PPP	 Change from baseline in PPPASI total score at week 16 Change from baseline in Palmoplantar Pustulosis Severity Index (PPSI) total score at week 16 Change from baseline in subject's Visual Analogue Scale (VAS) assessment for PPP symptoms (pruritus and pain/discomfort) at week 16 Change from Baseline in Dermatology Life Quality Index 			
		(DLQI) total score at week 16			
•	To evaluate the safety and tolerability of apremilast 30 mg BID compared with placebo in subjects with PPP	 Treatment-emergent adverse events (TEAEs), serious TEAEs, and TEAEs of interest Clinically significant changes in body weight, vital signs, and laboratory abnormalities 			

Primary Estimand

The main estimand of primary interest for the primary efficacy endpoint (i.e., achievement of PPPASI-50 response defined as at least 50% reduction from baseline in PPPASI total score, at week 16) is defined in terms of the following attributes:

- The target population of interest is Japanese subjects with PPP defined through the inclusion/exclusion criteria.
- The primary endpoint is the achievement of PPPASI-50 response at week 16.
- Intercurrent events (IEs) are investigational product (IP) discontinuation due to lack of efficacy, adverse event, or protocol-prohibited medication use. A subject will be considered a treatment failure after any of the IEs.
- The summary measure is the difference between apremilast 30 mg BID group and placebo group in proportion of responders based on the intent-to-treat (ITT) population including all randomized subjects.

A missing value after any of the IEs will be imputed as non-responders, otherwise, will be imputed with a multiple imputation (MI) method. A non-missing value after any of the IEs will also be imputed as non-responders.

Secondary Estimand(s)

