9.6.1 Analyses of Primary Safety Endpoint(s)

There is no primary safety endpoint. As a secondary endpoint, the safety and tolerability of apremilast 30 mg BID will be compared to placebo. No inferential testing for statistical significance will be performed for safety analyses.

Unless otherwise specified, the analyses of AEs and marked abnormalities (laboratory parameters and vital signs) for both the placebo-controlled period and apremilast-exposure period will be summarized by subject incidence rate. For safety summaries of apremilast-exposure period, the exposure-adjusted incidence rate will be presented to account for the difference exposure to the IP.

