For the summary of the new events of TEAE by exposure interval, each subject is counted once for either subject incidence or EAIR for each applicable specific TEAE in each exposure interval where an event started. The denominator of a subject incidence is the number of subjects with exposure time exceeding the lower bound of the particular exposure interval, while the denominator of an EAIR is the sum of the exposure time during the exposure interval (up to the first event start date for subjects with at least one event starting in the interval) among the same number of subjects as in the denominator of the corresponding subject incidence. The exposure time for a subject without the specific event is the treatment duration, whereas the exposure time for a subject with the specific event is the treatment duration up to the start date (inclusive) of the first occurrence of the specific event. For the summary of the first onset of TEAE by exposure interval, only the first onset of specific TEAE is considered for each subject.

Following TEAEs of interest will be summarized according to their categories and PT by severity (mild, moderate, severe), relationship, action taken with IP, fatality, and seriousness.

- Depression: MedDRA narrow scope SMQ of Depression (excluding suicide and self-injury)
- Serious infection: MedDRA primary SOC of Infections and infestations and the events assessed as serious
- Risk of Triggering Suicide: MedDRA narrow scope sub-SMQ of Suicide/selfinjury
- Serious Diarrhea, Nausea, and Vomiting: definition can be found in TFLSD.
- Malignancies: definition can be found in TFLSD.
- Vasculitis and Vasculopathy: MedDRA narrow scope SMQ of Vasculitis.
- Serious Hypersensitivity: MedDRA narrow scope SMQ of Hypersensitivity.
- Weight Change (Weight decrease): definition can be found in TFLSD.

Subject listings of AEs including non-treatment-emergent AEs will be provided.

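### The SAP's Serious Hypersensitivity category has no seriousness condition, so its count and exposure-adjusted rate would not match its label

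*SAP*

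**What the plan says.** The secondary safety endpoint in SAP Section 2.1 is "Treatment-emergent adverse events (TEAEs), serious TEAEs, and TEAEs of interest", together with clinically significant changes in weight, vital signs and laboratory values. Section 9.6.2 names eight categories of interest. Three carry the word serious in their label:

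- "Serious infection: MedDRA primary SOC of Infections and infestations and the events assessed as serious"
- "Serious Diarrhea, Nausea, and Vomiting: definition can be found in TFLSD"
- "Serious Hypersensitivity: MedDRA narrow scope SMQ of Hypersensitivity"

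Every category is to be "summarized according to their categories and PT by severity (mild, moderate, severe), relationship, action taken with IP, fatality, and seriousness". Section 9.6.1 plans subject incidence for adverse events, with exposure-adjusted incidence rates for the apremilast-exposure period, and states: "No inferential testing for statistical significance will be performed for safety analyses".

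The protocol defines seriousness in Appendix 4 (Section 11.4), in the note to the severity grading scale: "An event is defined as 'serious' when it meets at least 1 of the predefined outcomes".

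**The concern.** The label and the rule of one category disagree. A programmer who follows the rule selects every treatment-emergent event whose preferred term falls in the narrow SMQ, whether or not it was serious. A programmer who follows the label adds a filter that the SAP does not state. The two would produce different totals from the same data, and both could claim to have followed the plan.

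At stake is the figure most likely to be lifted out of the table: the category incidence and, for the apremilast-exposure period, its exposure-adjusted rate. If the rule is followed, that figure measures all hypersensitivity events in the SMQ under a heading that says serious. Serious infection, in the same list and under the same heading word, would be restricted to serious events, so the two could not be read on the same footing.

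**Working it through.** The plan gives no figure to reproduce. The check is a comparison of definitions, followed by what the literal rule does to the counts.

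**Step 1. The three serious categories side by side (SAP Section 9.6.2).**

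| Category | Term list given | Seriousness condition given | Defers to TFLSD |
|---|---|---|---|
| Serious infection | Yes, a primary SOC | Yes | No |
| Serious diarrhea, nausea, vomiting | No | No | Yes |
| Serious hypersensitivity | Yes, a narrow SMQ | No | No |

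The hypersensitivity line is the only one of the three that presents itself as complete and yet omits the condition.

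**Step 2. Can the SMQ supply the condition?** No. An SMQ selects preferred terms. Under Protocol Appendix 4, seriousness depends on the outcome of the individual event, so two events with the same preferred term can differ in seriousness. A term list cannot make that selection.

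**Step 3. Is the condition supplied elsewhere?** I found no other place in the protocol or SAP that supplies it. The TFLSD is not among the documents, and this line does not point to it.

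**Step 4. Effect on the count.** For one group of *n* subjects, let *a* be the number with at least one serious treatment-emergent event in the SMQ, and *b* the number with such events but none serious.

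- Count implied by the label: *a*
- Count produced by the rule: *a + b*
- Excess in incidence: *b / n*

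With the planned 85 per group (SAP Section 3.2), each subject in *b* adds 1/85 = 1.2 percentage points. The documents give no value for *a* or *b*.

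**Step 5. Effect on the exposure-adjusted rate.** The numerator rises from *a* to *a + b*. Section 9.6.2, in describing its exposure-interval tables, ends a subject's exposure time at the first occurrence of the event. If the category rate uses the same convention (an assumption), counting non-serious events can only shorten the person-time. The literal rate is then at least as high as the rate that the label implies.

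**The case against.** The best defence is that the label itself does the filtering: the heading says serious, the text after the colon gives the terms, and because seriousness belongs to the event, a reader would naturally apply both. This reading is possible, and the documents do not reveal what the sponsor intended. But it makes the explicit condition in the Serious infection line redundant. Where the authors applied the condition in this list, they wrote it down. At best the line is ambiguous. Read as written, it gives a count that its label does not describe.

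The planned split by seriousness does not show which reading was meant. It applies to all eight categories, including Serious infection, where it is redundant in any case.

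The second objection concerns consequences, and much of it stands. A reader might infer that a truly serious case would be lost among milder ones, or that the report would show a serious allergic risk that never occurred. The documents do not support either inference. Each category is broken down by preferred term and by seriousness, Section 9.6.2 also plans separate tables of serious and of serious drug-related events, and subject listings are provided. No event's seriousness is misrecorded. What can mislead is the category total, or its rate, when quoted without the breakdown.

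A reader might also suppose that the extra events would be mainly mild skin reactions, and put a rate on them. The documents neither list the terms in the SMQ nor give any frequency for them. All that can be said is that they would be non-serious events in the SMQ.

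**Conclusion.** The point holds as a mismatch between label and rule in one of the eight categories of interest. Followed literally, the rule gives a category total, and an exposure-adjusted rate, that include non-serious events under a serious heading and are not comparable with Serious infection.

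The reach is small. Safety is descriptive with no inferential testing, so the primary analysis, the type I error and the efficacy results are untouched. The serious subset can be recovered from other planned outputs. The size of the excess is *b / n*, which cannot be estimated from the documents; it is zero if no subject has only non-serious events in the SMQ.

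The conclusion assumes that the line is programmed as written and that the TFLSD does not already carry the missing condition. If it does, the SAP and the TFLSD differ and the SAP line still needs correcting.

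**What to change.** Decide which category was intended, then make label and rule agree before the tables are run:

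- If only serious events are meant, add to the hypersensitivity line the same seriousness condition that the Serious infection line carries.
- If all hypersensitivity events are meant, keep the SMQ rule and rename the category Hypersensitivity.
- If both are useful, show both as separate, correctly labelled categories.

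Make the TFLSD consistent with the choice. The cost is a few words in the SAP and one filter or one label in the program. The one decision that matters is intent: adding the filter when all events were meant would drop the non-serious events from the category, so that case calls for the rename or for both rows. Settling this beforehand also avoids the appearance of redefining a safety category after seeing its counts.

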9.6.3 Laboratory Test Results

Summary statistics of observed values and changes from baseline in the selected laboratory parameters will be provided over time. Frequency summary of shifts from baseline to the worst post-baseline value in terms of normal/abnormal will be provided. The selected laboratory parameters with abnormalities criteria are available in the Appendix A. For the purposes of the summary, subjects with abnormal (normal) values at baseline are defined as those whose baseline value is low (not low) for criteria concerning low values and those whose baseline value is high (not high) for criteria concerning high values; both low and high are relative to the laboratory normal range.

Individual subject data of all laboratory data will be listed and values outside of the normal reference range will be flagged.

9.6.4 Vital Signs

The analyses of vital signs including summary statistics **of observed values and changes from baseline** over time will be provided. Frequency summaries of shifts from baseline to the worst post-baseline value in terms of normal/abnormal(low/high) will be provided for **heart rate** and blood pressure. Normal ranges are defined as: 60-90 mmHg for diastolic blood pressure, 90-140 mmHg for systolic blood pressure, and 60-100 beats/minute for **heart rate**.

A subject data listing of all vital signs will be provided.

9.6.5 Physical Measurements

The **observed values and** change from baseline for weight and BMI will be summarized.

A subject data listing of physical measurements will be provided.

9.6.6 Exposure to Investigational Product

Descriptive statistics will be produced to describe the exposure to IP by treatment group. Treatment duration (in weeks) is calculated as (the date of the last dose of IP – the date of the first dose of IP + 1)/7. Summary statistics for treatment duration (in weeks), as well as a frequency summary of treatment duration categories (placebo-controlled period: < $4, \ge 4$ to < $8, \ge 8$ to < $12, \ge 12$ to < $16, \ge 16$, active treatment period: ≥ 16 to < $20, \ge 20$ to < $24, \ge 24$ to < $32, \ge 32$ to < $44, \ge 44$ to < $52, \ge 52$ weeks) will be provided.

Treatment duration for apremilast-exposure period is calculated from the date of the first apremilast administered, which is the date of the first administration of apremilast on/after the randomization at week 0 (visit 2) or switched to apremilast at week 16 (visit 8), to the last apremilast administered date of subjects who discontinue before the study completion or who complete the study at week 52 (visit 13).

For treatment compliance, descriptive statistics will be provided. The treatment compliance (%) for each subject will be computed as 100 times the total number of tablets actually taken (sum of dose per administration) over the period divided by the intended total number of tablets that should have been taken over the same period. It is assumed that a subject takes 2 tablets per day from the first through the last IP administered date.

A subject data listing of IP administration will be provided.

9.6.7 Exposure to Prior/Concomitant Medication and Procedures

Prior medications and procedures are defined as medications that were started before the start of the study treatment and either ended before the start of the study treatment or continued after study treatment. Concomitant medications and procedures are defined as medications that were either initiated before the first dose of IP and continued during the study treatment or initiated on/after the date of the first dose of IP and on/before the date of treatment discontinuation. Medications and procedures initiated prior to the start of study treatment and were continued after the start of study treatment will be counted as both prior and concomitant medications and procedures.

Number and proportion of subjects receiving prior/concomitant medications and procedures will be summarized by preferred term or category for each treatment group as coded by the World Health Organization Drug dictionary. The prior **and concomitant** medications for PPP, focal infection and PAO will be summarized.

A subject listing of prior and concomitant medications and procedures will be provided.

9.7 Other Analyses

PK and Biomarker analyses are planned separately.

9.7.1 Analyses of Pharmacokinetic Endpoints

Detailed descriptions of PK analysis will be documented separately.

9.7.2 Analyses of Biomarker Endpoints

Detailed descriptions of biomarker analysis will be documented separately, and the result will be separately reported.

10. Changes From Protocol-specified Analyses

Added additional exploratory endpoints:

Table 10-1. Additional Exploratory Emcacy Endpoint Summary Table				
Endpoint	Summary and Analysis Method			

Table 10-1. Additional Exploratory Efficacy Endpoint Summary Table

11. Literature Citations / References

van Hout B, Janssen MF, et al. Interim scoring for the EQ-5D-5L: Mapping the EQ-5D-5L to EQ-5D-3L value sets. Value in Health 2012 Jul-Aug;15(5):708-15

12. Prioritization of Analyses

Not applicable

13. Data Not Covered by This Plan

A detailed description of PK and biomarker analysis will be documented separately.

14. Appendices

Appendix A. Criteria for Marked Changes in Laboratory Values

Category	Analyte	Abnormality Criteria	
Chemistry	Sodium	>150, <130 mmol/L	
	Potassium	>5.5, <3.0 mmol/L	
	Albumin	<25 g/L	
	Calcium	>3.0, <1.8 mmol/L	
	Magnesium	> 1.2 mmol/L	
	Phosphorus	>1.60, <0.64 mmol/L	
	Glucose	>13.9, <2.8 mmol/L	
	BUN or Urea *Blood Urea Nitrogen	> 24 mmol/L	
	Creatinine	>1.5×ULN umol/L	
	Uric acid	> 480 umol/L	
	Total bilirubin	>1.8×ULN umol/L	
	ALP *Alkaline Phosphatase	>400 U/L	
	LDH *Lactate Dehydrogenase	> 2xULN U/L	
	AST (SGOT) *Aspartate Aminotransferase	>3.0×ULN U/L	
	ALT (SGPT) *Alanine Aminotransferase	>3.0×ULN U/L	
	Cholesterol	> 7.8 mmol/L	
	Triglycerides	> 3.4 mmol/L	
Hematology	Hemoglobin	>150, <110 g/L	
	Platelets	>600, <75 10^9/L	
	WBC *Leukocytes	< 2.0 10^9/L	
	Lymphocytes	<0.8 10^9/L	
	Neutrophils, Segmented	< 1.5 10^9/L	

Appendix B. Analytical Windows

Per protocol, visits are to be performed within 2 days of the protocol-specified study day for placebo-controlled period, and within 4 days for the active treatment period. To allow for variations in scheduling, the following visit windows will be applied to selected efficacy evaluations to assign a most appropriate nominal visit for analysis. If more than one assigned visit falls within the same defined window, the closest visit to the target day (ie, scheduled visit week × 7 + 1) will be considered for analysis. If two assessment dates are the same distance from the target day, then the latest visit will be considered for analysis.

Vital Signs and Physical Measurement

Visit Week	Target Day	Window Definition
Week 0 (Visit 2: Baseline)	1	Last Evaluation prior to or on Study Day 1
Placebo-controlled Period	-	
Week 2 (Visit 3)	15	Study Day 2 – 22
Week 4 (Visit 4)	29	Study Day 23 – 36
Week 6 (Visit 5)	43	Study Day 37 – 50
Week 8 (Visit 6)	57	Study Day 51 – 71
Week 12 (Visit 7)	85	Study Day 72 – 99
Week 16 (Visit 8)	113	Study Day 100 – End of the Period
Active Treatment Period		
Week 20 (Visit 9)	141	One day after the first apremilast dosing day on Visit 8* – 155
Week 24 (Visit 10)	169	Study Day 156 – 197
Week 32 (Visit 11)	225	Study Day 198 – 267
Week 44 (Visit 12)	309	Study Day 268 – 337
Week 52 (Visit 13)	365	Study Day 338 – End of the Period

Analysis window for Subject's VAS assessment for PPP symptom for palms and soles

Visit Week	Target Day	Window Definition
Week 0 (Visit 2: Baseline)	1	Last Evaluation prior to or on Study Day 1
Placebo-controlled Period		
Week 2 (Visit 3)	15	Study Day 2 – 22
Week 4 (Visit 4)	29	Study Day 23 – 36
Week 6 (Visit 5)	43	Study Day 37 – 50
Week 8 (Visit 6)	57	Study Day 51 – 71
Week 12 (Visit 7)	85	Study Day 72 – 99
Week 16 (Visit 8)	113	Study Day 100 – End of the Period
Active Treatment Period		

Visit Week	Target Day	Window Definition
Week 24 (Visit 10)	169	One day after the first apremilast dosing day on Visit 8 – 197
Week 32 (Visit 11)	225	Study Day 198 – 295
Week 52 (Visit 13)	365	Study Day 296 – End of the Period

Analysis window for DLQI, and Laboratory Test

Visit Week	Target Day	Window Definition			
Week 0 (Visit 2: Baseline)	1	Last Evaluation prior to or on Study Day 1			
Placebo-controlled Period					
Week 8 (Visit 6)	57	Study Day 2 – 85			
Week 16 (Visit 8)	113	Study Day 86 – End of the Period			
Active Treatment Period					
Week 24 (Visit 10)	169	One day after the first apremilast dosing day on Visit 8 – 197			
Week 32 (Visit 11)	225	Study Day 198 – 225			
Week 52 (Visit 13)	365	Study Day 226 – End of the Period			

Active treatment period start point for adverse event data shall be the first apremilast dosing day on Visit 8.

Appendix C. Handling of Dates, Incomplete Dates and Missing Dates Imputation Rules for Partial or Missing Start Dates

		Stop Date						
		Complete: yyyymmdd		Partial: yyyymm		Partial: УУУУ		Missing
Start Date		< 1 st dose	≥ 1 st dose	< 1 st dose	≥ 1 st dose	< 1 st dose	≥ 1 st dose	
				уууутт	уууутт	уууу	уууу	
Partial:	= 1 st dose yyyymm	2	1	n/a	1	n/a	1	1
уууутт	≠ 1 st dose		2	2	2	2	2	2
	уууутт					,		
Partial:	= 1 st dose		1		1	n/a	1	1
уууу	уууу	3		3				
	≠ 1 st dose		3		3	3	3	3
	уууу							
Mis	sing	4	1	4	1	4	1	1

The reference date for the following rules is the date of first dose of apremilast.

1=Impute the date of first dose; 2=Impute the first of the month; 3=Impute January 1 of the year; 4=Impute January 1 of the stop year

Note: For subjects who were never treated (first dose date is missing), partial start dates will be set to the first day of the partial month or first day of year if month is also missing.

Imputation Rules for Partial or Missing Stop Dates

Initial imputation

- If the month and year are present, impute the last day of that month.
- If only the year is present, impute December 31 of that year.
- If the stop date is entirely missing, assume the event or medication is ongoing.

If the imputed stop date is before the start date, set stop date to missing.

If the imputed stop date is after the death date, impute as death date.

Imputation Rules for Partial or Missing Death Dates

If death year and month are available but day is missing:

- If yyyymm for the date last known to be alive equals yyyymm for death date, set death date to the day after the date last known to be alive.
- If yyyymm for the date last known to be alive is less than the yyyymm for death date, set death date to the first day of the death month.
- If yyyymm for the date last known to be alive is greater than yyyymm for death date, assume date last known to be alive is in error, set death date to the first day of the death month.

If month and day are missing and year of death is known:

- If yyyy for the date last known to be alive equals yyyy for death date, set death date to the day after last known to be alive date.
- If yyyy for the date last known to be alive is less than yyyy for death date, set death date to the first day of the death year.
- If yyyy for the date last known to be alive is greater than yyyy for death date, assume date last known to be alive is in error, set death date to the first day of the death year.

If a death date is totally missing:

• Set death date to the day after the date last known to be alive. If the date last known to be alive is a partial date, set it to the first day of the month last known to be alive or first day of the year last known to be alive if month is also missing.

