8.1.2 Treatment Period

Visits will occur per the Schedule of Activities (Table 1-1). On-study visits may be completed as specified in the Schedule of Activities. The date of the first dose of apremilast is defined as day 1. All subsequent doses and study visits will be scheduled

Protocol Number: 20200195

Date: 15 April 2022 Page 44 of 99

based on the day 1 date. Apremilast is to be administered during each visit that it is required.

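### The DLQI and laboratory window for week 32 closes on its own target day, so compliant week-32 results taken 1 to 4 days late are labelled week 52

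*SAP*

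**What the plan says.** SAP Appendix B maps each assessment to a nominal visit by study day. The target day is defined as "scheduled visit week × 7 + 1". Actual visits are expected within 2 days of schedule in the placebo-controlled period "and within 4 days for the active treatment period"; Protocol Table 1-1 gives the same allowance. Protocol Section 8.1.2 counts visits from day 1, the first dose. A tie-break covers duplicates: "If more than one assigned visit falls within the same defined window, the closest visit to the target day" is the one analysed.

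The appendix has three tables. Two of them have the same active-period visits (weeks 24, 32 and 52) but place the boundary between weeks 32 and 52 differently:

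- **VAS:** week 32 is "Study Day 198 – 295", and week 52 begins on day 296.
- **DLQI and laboratory tests:** week 32 is "Study Day 198 – 225", and week 52 is "Study Day 226 – End of the Period".

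Protocol Table 1-1 schedules DLQI and laboratory tests at weeks 24, 32 and 52, with neither at week 44.

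**The concern.** A window that ends on its own target day has no room for a late visit. A subject seen one day after the week-32 target, well inside the allowance, has that day's DLQI and laboratory results labelled week 52.

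What happens next depends on whether the subject stays in the study:

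- **Subject reaches week 52.** Both records fall in the week-52 window. The closest-to-target rule keeps the true week-52 record, so the compliant week-32 value disappears from the by-visit summaries and week 32 is blank for that subject.
- **Subject stops before week 52.** The late week-32 record, or an end-of-treatment record (Visit 13/ET) from day 226 onward, can be the only one in the window, or the closest to day 365. It is then reported as week 52.

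Week 32 therefore loses valid data, and week 52 takes in early data selectively from subjects who dropped out. SAP Section 9.6.3 calls for laboratory values and changes from baseline to be summarised over time, so these labels determine what the long-term by-visit laboratory tables show.

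**Working it through.** **Inputs.** The target-day formula, visit allowance and windows come from SAP Appendix B. The assessment schedule comes from Protocol Table 1-1.

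**Target days** (week × 7 + 1):
- Week 24: 24 × 7 + 1 = 169
- Week 32: 32 × 7 + 1 = 225
- Week 52: 52 × 7 + 1 = 365

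These reproduce the SAP's own target days.

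**How the other bounds are built.** The SAP states no rule for the bounds, so each numeric upper bound was compared with the midpoint of its target day and the next one in the same table.

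| Table | Upper bounds in the SAP | Equal to midpoint |
|---|---|---|
| Vital signs and physical measurement | 22, 36, 50, 71, 99, 155, 197, 267, 337 | 9 of 9 |
| VAS | 22, 36, 50, 71, 99, 197, 295 | 7 of 7 |
| DLQI and laboratory | 85, 197, 225 | 2 of 3 |

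In total 18 of 19 match. The exception is DLQI and laboratory week 32: the SAP has 225, and the midpoint is (225 + 365) / 2 = 295, which is the VAS figure. The change from week 16 to the first active-period visit is set by the dosing day at Visit 8, not by a fixed study day, so it is not part of this comparison.

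**Compliant week-32 visits.** 225 − 4 = 221 and 225 + 4 = 229, which gives 9 permitted days.

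| Study day | Label as written | Days from 225 | Days from 365 | Label with bound 295 |
|---|---|---|---|---|
| 221–225 | Week 32 | 4 to 0 | 144 to 140 | Week 32 |
| 226 | Week 52 | 1 | 139 | Week 32 |
| 227 | Week 52 | 2 | 138 | Week 32 |
| 228 | Week 52 | 3 | 137 | Week 32 |
| 229 | Week 52 | 4 | 136 | Week 32 |

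Four of the 9 permitted days are misassigned.

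**Share of records.** The documents give no distribution of visit days. If visits were spread evenly over the allowance, 4/9 = 44% of on-schedule week-32 records would be mislabelled. The possible range is 0% (every visit on or before day 225) to 100% (every visit 1 to 4 days late).

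**Full extent of the mislabelled span.** Days 226 to 294, that is 294 − 226 + 1 = 69 days, are strictly closer to day 225 than to day 365 yet carry the week-52 label. Day 295 is a tie.

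**The case against.** The two cells do conflict with the VAS table and with the visit allowance, and nothing in the schedule explains it. The bounds 225 and 226 meet without gap or overlap, so the text does not look damaged and would be programmed as it stands. The best case on the other side is that little depends on it.

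- **Reach.** This stands. The safety objective compares apremilast with placebo, and that comparison ends at week 16, where the windows are sound. SAP Section 9.1 plans no between-group analysis in the active period, and safety has no inferential testing. Shifts to the worst post-baseline laboratory value and the incidence of marked abnormalities, as described, do not depend on a visit label, and all laboratory data are listed. For DLQI, the only analysis specified in the readable text is at week 16; later summaries are inferred from Section 9.1 and from the window table itself.
- **The 44% figure.** It rests on evenly spread visits. Only 4 of 9 permitted days follows from the documents.
- **Dropouts in week 52.** A corrected window would still open on day 296, 365 − 296 = 69 days before target, and would still admit some end-of-treatment results. The error moves that opening back to day 226 (139 days before target); it does not create the feature.
- **A trade-off in the fix.** With a bound of 295, an end-of-treatment result on days 226 to 295 falls in week 32 and gives way to an on-schedule week-32 result if there is one. That is the closest-to-target rule working as intended, and the value remains in the listings.

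These points limit the consequence. None of them defends the bound of 225.

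**Conclusion.** The concern holds. Followed as written, the DLQI and laboratory table assigns visits 1 to 4 days after the week-32 target to week 52, although the plan treats them as on schedule. The certain size is 4 of the 9 permitted days, and 69 study days in all that lie closer to week 32 but are labelled week 52. The proportion of records affected cannot be known from the documents.

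The damage is confined to descriptive by-visit DLQI and laboratory summaries at weeks 32 and 52. The primary endpoint, the week-16 secondary endpoints, type I error control and the worst-value laboratory outputs are not affected. The likely cause is that the target day was typed in place of 295. That is an inference from the other 18 bounds and the VAS table, because the SAP does not state a midpoint rule. The point should be corrected, since the summaries would otherwise be wrong as specified.

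**What to change.** In the DLQI and laboratory table of SAP Appendix B, change two cells to match the VAS table:

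- Week 32 (Visit 11): Study Day 198 to 295.
- Week 52 (Visit 13): Study Day 296 to the end of the period.

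Every compliant week-32 day, 221 to 229, then maps to week 32. A sentence stating that fixed boundaries are midpoints between adjacent target days, with the midpoint day going to the earlier visit, would make the rule explicit.

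The cost is two cells and the matching lines of the windowing program, ideally before any week-32 summary is produced. Visits, data collection and confirmatory testing do not change. The one side effect is that some end-of-treatment results on days 226 to 295 will give way to an on-schedule week-32 result in the by-visit tables.
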